9.2. Reporting Period

The adverse event reporting process will commence upon signing informed consent according to the rules below.

- SAE:
SAE reporting will commence from the time the participant provides informed consent through last patient visit at follow-up. Any SAE occurring after the reporting period must be promptly reported if a causal relationship to study treatment is suspected.
- Events associated with study-specific procedures:
Events associated with study-specific procedures prior to initial administration of study drug will be tracked as AEs from the time when the study participant signed the ICF. The study-related procedure might include discontinuation from or decrease in current therapy, a study-specific assessment or scale, or a study-specific procedure.
- Non-serious AEs not related to study procedures:
 - Non-serious AEs not related to study procedures that occur **prior** to the first dose of study drug will be captured under medical history
 - Non-serious AEs not related to study procedures that occur **after** the first dose of study drug will be captured as TEAEs
- Adverse events reported during the single-blind placebo-run-in period will be captured as having onset after first dose of single-blind placebo administration but before first dose of double-blind study medication. Adverse events reported during the double-blind treatment period will be captured as having onset after first dose of double-blind study medication. The appropriate box corresponding to the period in which the TEAE occurred should be ticked in the CRF.

9.3. Assessment of Severity

The following definitions of severity should be used in the evaluation of AEs:

- Mild: an AE that is easily tolerated and does not interfere with daily activities.
- Moderate: an AE that is sufficiently discomforting so as to interfere with daily activities.
- Severe: an AE that prevents normal everyday activity.

9.4. Assessment of Relationship to Study Drug

The Investigator's assessment of causality must be provided for all adverse events (serious and non-serious); the Investigator must record the causal relationship in the EDC. An Investigator's causality assessment is the determination of whether there exists a reasonable possibility that the investigational product caused or contributed to an adverse event. If the Investigator does not know whether or not investigational product caused the event, then the event will be handled as "related to investigational product" for reporting purposes, as defined by the Sponsor. If the Investigator's causality assessment is "unknown but not related to investigational product", this should be clearly documented on study records.

In addition, if the Investigator determines a serious adverse event is associated with study procedures, the Investigator must record this causal relationship in the source documents and EDC, as appropriate, and report such an assessment in accordance with the serious adverse event reporting requirements, if applicable.

The following definitions of relationship to study drug should be used to characterize the suspected causality of each AE, based on the Principal Investigator's or licensed physician consideration of all available information:

Related: A direct cause and effect relationship between the AE and the study drug is reasonably related to the study drug in the judgment of the investigator.

Not Related: The AE is not reasonably related to the study drug in the judgment of the investigator.

9.5. Serious Adverse Events

An SAE is any AE that is fatal or life-threatening (see below), results in persistent or significant disability (see below) or incapacity, requires inpatient hospitalization or prolongation of an existing hospitalization, or is a congenital anomaly/birth defect.

Other important medical events that may not result in death, be life-threatening, or require hospitalization should also be considered SAEs when, based upon appropriate medical judgment, they may jeopardize the study participant and may require medical or surgical intervention to prevent one of the outcomes listed above. Examples of such medical events include allergic bronchospasm requiring intensive treatment in an emergency room or at home, blood dyscrasias or convulsions that do not result in inpatient hospitalization.

9.5.1. Life Threatening Adverse Events

A life-threatening AE is any AE that, in the view of the PI or designated licensed physician, places the study participant at immediate risk of death from the reaction as it occurred. A life-threatening AE would not be an AE that, had it occurred in a more serious form, might have caused death. For example, drug-induced hepatitis that resolved without evidence of

hepatic failure would not be considered life-threatening even though drug-induced hepatitis can be fatal.

9.5.2. Disability

Disability is defined as a substantial disruption of a person's ability to conduct normal life functions.

9.5.3. Unexpected Adverse Event

An unexpected adverse drug experience is defined as “any adverse drug experience, the specificity or severity of which is not consistent with the current IB. For example, under this definition, hepatic necrosis would be unexpected (by virtue of greater severity) if the IB only referred to elevated hepatic enzymes or hepatitis. Similarly, cerebral thromboembolism and cerebral vasculitis would be unexpected (by virtue of greater specificity) if the IB only listed cerebral vascular accidents. Unexpected, as used in this definition, refers to an adverse drug experience that has not been previously observed (e.g., included in the IB), rather than from the perspective of such experience not being anticipated from the pharmacological properties of the pharmaceutical product.”⁵

Serious and Unexpected adverse events (SUSARs) should be reported to the IRB as per IRB reporting requirements.

9.6. Documentation of Adverse Events

The condition of each study participant will be monitored throughout the study. Signs and symptoms of possible AEs may be observed by the staff, elicited by asking an open or indirect question (e.g., “How have you been feeling?”), or volunteered by the study participant. All AEs, whether observed by the PI or study site staff, elicited from the study participant, or volunteered by the study participant, will be recorded on the adverse event page(s) of the CRF. Data will include start and end dates, concomitant medications given for the AE, PI-specified or designated licensed physician-specified severity, relationship to study drug, and action taken. All AEs should be reported to the Study Sponsor.

9.7. Reporting Requirements

Follow-up of any ongoing AE (including any clinically significant laboratory abnormality) should be conducted as follows:

- If the Investigator determines the AE is *not related* to the study product or study procedures, the AE will be followed until resolution, or 60 days from end of study participation.
- All AEs with a relationship other than *not related* will be followed until

resolution, or until the patient is lost to follow-up.

At the discretion of the Investigator or designated licensed physician and Medical Monitor, the length of AE follow-up may be attenuated, with written rationale by the Investigator or designated licensed physician.

9.7.1. Serious Adverse Events Reporting Requirements

Knowledge of an SAE occurring or worsening in a patient at any time during the trial must be reported within 24 hours to the Sponsor. The Study Site is responsible for reporting the event to the relevant IRB in accordance with the IRB's specific requirements for reporting SAEs. The PI or designee should not wait to receive additional or follow-up information before an initial notification is made to the Sponsor.

Instructions related to SAE reporting, along with reporting forms, will be provided by the Sponsor to the Study Site and should be maintained in the Study Site File (SSF).

Reports relative to the patient's subsequent course must be submitted to the Sponsor until the event has subsided or, in the case of permanent impairment, until the condition stabilizes. These reports need not be submitted within 24 hours of first knowledge of each item of new information, unless the new information results in a change in diagnosis or represents a significant worsening of the patient's condition.

The PI or designee should immediately notify the Sponsor and the IRB if he/she learns of any post-study serious adverse event, which in his/her opinion is reasonably possibly related to the use of the study drug.

9.8. Adverse Events of Special Interest

9.8.1. Monitoring of MACE Events

Major adverse cardiac events (MACE) will be tracked in Part 1 and 2. For this study, a MACE event is defined as one of the following:

- Cardiovascular mortality
- Myocardial infarction
- Stroke.

It is not expected there will be an adequate number of MACE events to support reasonable statistical analysis, and it is not expected that there will be many MACE events. If and when the number of MACE events exceeds 10 for the study, a cardiovascular endpoints committee (CEC) will be convened to adjudicate MACE events, provided less than 90% of the study visits have occurred. If there are 10 or fewer MACE events in the study as of an advanced stage of the study (when it is 90% over, based on planned study visits), it will be deemed unnecessary to convene the CEC.

9.8.2. Documenting and Reporting of Hypoglycemia

Hypoglycemia is of special concern in this population and should be described to the patients. Home glucose monitoring must be undertaken in the event patients experience symptoms of hypoglycemia. Patients should be instructed on self-management of a hypoglycemic episode (e.g., prompt ingestion of carbohydrates).

For the Sentinels, any episode of hypoglycemia associated with symptoms must be captured on the patient's diary and in the EDC as an AE with symptoms and contemporaneous glucose measurements if they are available.

For Part 1 and Part 2, hypoglycemic adverse events will be assessed and reported in three categories:

- **severe hypoglycemia** (**each** of the following criteria **must** be met):
 - The patient was unable to treat him/herself, requiring the assistance of another person to actively administer carbohydrate, glucagon, or other resuscitative actions. Neurologic impairment must be the explanation for why the patient could not treat him/herself and required the assistance of another person.
 - Blood glucose:
 - If blood glucose was measured and was ≤ 49 mg/dL (2.7 mmol/L) using plasma referenced- home glucometers, CGM (or central laboratory), **or**
 - If blood glucose was not measured, the clinical manifestations were reversed by oral carbohydrates, subcutaneous glucagon, or intravenous glucose.
- **documented symptomatic** hypoglycemia if typical symptoms **are** accompanied by measured glucose ≤ 70 mg/dL using plasma-referenced home glucometers (or central laboratory) or
- **probable symptomatic** hypoglycemia if typical symptoms are not accompanied by a glucose determination as described above but are presumably caused by a plasma concentration ≤ 70 mg/dL.

Treatment should be discontinued for a patient following an episode of severe hypoglycemia, if in the investigator's judgment the episode was both:

- unexpected with no substantial aggravating issues precipitating the episode
- unavoidable in the future, through dose adjustments of insulin and patient education.

Episodes of severe hypoglycemia will be evaluated by an independent data monitor in Part 1

and Part 2.

- Events that do **not** meet the criteria for severe hypoglycemia will be characterized as mild or moderate in severity.

Reporting of Hypoglycemia

Hypoglycemia will be reported following the classification published by the International Hypoglycaemia Study Group⁶ as follows:

Severe hypoglycemia (level 3):

In order to be considered **severe** hypoglycemia **each** of the following criteria **must** be met:

1. The patient was unable to treat him/herself, requiring the assistance of another person to actively administer carbohydrate, glucagon, or other resuscitative actions.
Neurologic impairment must be the explanation for why the patient could not treat him/herself and required the assistance of another person.
2. Blood glucose:
 - a. If blood glucose was measured and was ≤ 49 mg/dL (2.7 mmol/L) using plasma referenced- home glucometers, CGM (or central laboratory), **or**
 - b. If blood glucose was not measured, the clinical manifestations were reversed by oral carbohydrates, subcutaneous glucagon, or intravenous glucose.

Clinically important hypoglycemia (level 2):

A glucose level of less than 54 mg/dl (3.0 mmol/l) with or without typical symptoms of hypoglycemia. This will be quantified as:

- The percentage of CGM values that are below the threshold of <54 mg/dL [3.0 mmol/L] or the number of minutes or hours below these thresholds.
- As the number of hypoglycemic events that occur over the given CGM reporting period

A hypoglycemic event should be defined as follows:

- Beginning of a CGM event: readings below the threshold for at least 15 min is considered an event. For example, at least 15 min <54 mg/dL (3.0 mmol/L) to define a clinically significant (level 2) hypoglycemic event.
- End of a CGM event: readings for 15 min at ≥ 70 mg/dL (3.9 mmol/L).
- A second hypoglycemic event outcome of prolonged hypoglycemia is considered when CGM levels are <54 mg/dL (3.0 mmol/L) for consecutive 120 min or more.

Glucose alert value (or level 1):

A glucose value of 70–54 mg/dL (3.9–3.0 mmol/L) with or without symptoms. This will be quantified as the percentage of CGM values between 70–54 mg/dL (3.9–3.0 mmol/L) or the number of minutes or hours between these thresholds.

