Registration	X									
Enrollment			X							
Randomization				X						
Collect demographic information	X									
Review of Inclusion/Exclusion Criteria	X		X	X						
Medical history/ AE monitoring	X		X	X	X	X	X	X	X	X
Concomitant Medication history/update	X		X	X	X	X	X	X	X	X
Physical exam	X ¹			X ²					X ²	X ²
Body weight	X		X	X	X	X			X	X
Sitting vitals and blood pressure	X		X	X ⁴	X	X			X	X
Supine 12-lead ECG	X		X	X ⁵	X	X			X	X
Clinical chemistry, hematology, lipids and glycemic markers ³	X			X ³	X	X			X	X
Collect PK samples ⁶				X		X			X	X
Collect retention samples (optional, exploratory)				X		X			X	X
Collect urine for urinalysis	X			X	X	X			X	X
Collect urine for pregnancy test ⁷	X ⁷		X	X ⁷	X	X	X	X	X	X ⁷
Administer DTSQs	X									
Administer DTSQc										
Ask QOL question and enter answer in EDC										
Provide glucometer and glucometer strips, if needed ⁸		X	X	X	X	X	X			
Provide insulin dosing collection device (if needed) ⁹		X	X							
Apply Sponsor CGM			X					X		
Collect and Review Sponsor CGM ¹⁰				X					X	X
Collect insulin dosing data and glucose data needed for insulin adjustment ¹¹		X	X	X	X	X	X	X		X
Administer study drug with morning meal ¹²			X	X						
Collect unused drug/compliance check (via pill count)				X	X	X	X	X		X
Dispense blinded study medication based on IWRS			X	X	X	X	X			
Contact patient by telephone or text ¹³		X	X	X		X	X			

¹ Full physical exams, including height, are to be conducted at Screening² Limited physical exams will be conducted at Week 0 and Week 12 and ET (if applicable)³ Refer to Laboratory Manual for Sample Collection Instructions and Appendix 2 (Part 2); At Week 0/Day 1 visit confirm patient is fasted prior to labs. Reschedule visit if subject is not fasted.⁴ Baseline vitals obtained in triplicate, prior to dosing on Week 0, single readings all other visits except Week 10 (no vitals)⁵ Baseline ECG obtained in triplicate, prior to dosing on Week 0, single readings all other visits except Week 10 (no ECGs)⁶ Blood samples will be obtained for TTP399 concentrations prior to dosing if dosing is conducted at visit⁷ Urine pregnancy tests should be conducted for all females at Screening, Week 0 and F/U. Urine pregnancy tests for WCBP are required

CONFIDENTIAL

Investigational Product: TTP399
Protocol Number: TTP399-203

Amendment5/FINAL
Date: 08FEB2019

at all visits.

⁸ Glucometers and related supplies will be supplied to patients who don't have CGM devices or have CGM devices that require calibration.

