The unblinded CGM is required throughout Part 1 to monitor patient safety and patients must agree to share their CGM data through the Dexcom CLARITY® software with the PI or designee and allow a de-identified copy to be shared with vTv. Patients must agree to share CGM data collected up to a month prior to the screening visit *with the site* for evaluation of glycemic control and insulin adjustment needed prior to the placebo run-in period. Unblinded CGM will be collected beginning with screening and continuing through the follow-up visit for patients in Part 1.

Patients enrolled in the Part 1 of the study should record the following in their CGM App:

- Home glucometer measurements undertaken in the event the patient experiences symptoms of hypoglycemia (entered in CGM as calibration)
- Events such as extreme stress or strenuous physical activity that are associated with hypoglycemic or hyperglycemic symptoms

Part 2 Patients

At the Week -2 and Week 10 visit, patients enrolled in Part 2 will be provided with a CGM device (sponsor provided, blinded). The CGM device will be collected at the following visit (Week 0/Day1 and Week 12, respectively). The CGM data will be collected during these periods: Baseline (Week -2 to Week 0) and from Week 10 to Week 12.

If the patient also has a personal CGM, the sponsor provided CGM will be the one of record for statistical analysis.

The sponsor will provide glucometers and related glucometer supplies, as needed.

If the basal insulin dose adjustment period is needed, the patients should collect fasting/pre-meal glucose values as instructed by the study site staff for evaluation. Glucose values can be collected either using personal CGMs or glucometers provided by the sponsor. For individuals who do not have personal CGMs, sponsor provided glucometers should be used

to collect glucose values.

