8.11. Management of Patients' Glycemic Control and Insulin Dose Adjustments

Patients will be counseled on identification and management of hypoglycemia and hyperglycemia. Glucose levels will be monitored using unblinded continuous glucose monitoring (if patients already have CGM) and self-monitoring of blood glucose using glucometers if unblinded CGM glucose values are not available. **Sentinel** patients are required to have a good hypoglycemic awareness and live with someone who has a good hypoglycemia awareness.

Parts 1 and 2, only

Prior to the placebo run-in period, the PI or designee will determine if the patient's basal insulin dose needs to be optimized to meet the fasting/pre-meal glucose target generally from 80-130mg/dL. If the PI determines that basal insulin dose adjustment is needed, the PI or designee, in collaboration with the patient, will optimize the basal insulin dose for up to 3 weeks prior to the placebo run-in period. If basal insulin dosing is adequate, the patient will move directly into the placebo-run in period. (See Figure 6 below).

Figure 6: Decision Flow Chart for Patient Visits Prior to Randomization

*Adjust basal insulin to target fasting/pre-meal glucose levels generally between 80-130 mg/dL

The PI or designee will use the following guidance in combination with the recent glucose data to instruct the patient on insulin adjustments needed.

BASAL INSULIN DOSE ADJUSTMENT PERIOD (up to 3 weeks before Week -2)

The PI or designee will review the past 14 days of CGM data (Part 1) or fasting/pre-meal glucose levels for the past 7 days using either CGM or glucometer data (Part 2) and determine if a basal insulin dose adjustment period is needed.

If basal insulin adjustments are needed, the basal rate should be assessed and adjusted to target fasting/pre-meal glucose levels generally between 80-130 mg/dL

If Low Blood Glucose: Make immediate insulin adjustment.

If Elevated Blood Glucose: Verify trends 2–3 days before adjusting insulin.

DURING PLACEBO RUN-IN PERIOD (2 weeks prior to randomization)

Do not make insulin adjustments except in response to safety concerns.

Record in the EDC:

- CSII: basal rate, Active Insulin Time and type of Pump, ICF and ICR
- MDI: basal insulin dosing information, ICR and ISF

DURING DOUBLE-BLIND PERIOD:**First day of dosing (Week0/Day 1):**

Reduce bolus insulin:

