7.7 Analysis of Safety Data

7.7.1 Adverse Events

Adverse events reported in this study will be coded using MedDRA®, Version 21.0 or later. Coding will be to the lowest level terms (LLT). The verbatim text, the preferred term, and the primary SOC will be listed in subject listings. Summaries that include frequencies and proportions of subjects reporting AEs will include the preferred terms and the SOCs.

Adverse event summaries will be done by study phase: (1) pre-dose,(2) placebo run-in, and (3) double-blind treatment phase, (4) period beginning with the first dose of double-blind medication, including follow-up phase. The final category is considered the primary summary of TEAEs to support comparisons of TTP399 with placebo.

Adverse events summaries will be constructed displaying AEs in decreasing order of total frequency according to the numbers of subjects reporting the AE (not the number of reports).

- Number (percent) of subjects reporting TEAE by Treatment and overall in accordance.

A listing will be constructed that includes the subject identification, the dose group, TEAEs, MedDRA terms, seriousness, severity, causality related to study medication, causality related to insulin, elapsed time to onset, duration, and outcome.

Adverse events of special interest (AESI) will include diabetic ketoacidosis and hypoglycemia.

For purposes of analysis and reporting, hypoglycemia events will be limited to those in the first two categories (severe hypoglycemia and documented symptomatic hypoglycemia) in accordance with FDA's regulatory guidance *Guidance for Industry Diabetes Mellitus: Developing Drugs and Therapeutic Biologics for Treatment and Prevention* (CDER, February 2008).

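### Non-severe symptomatic hypoglycemia seen only on CGM is left out of the categorized hypoglycemia analysis, so the count depends on the patient's glucose device

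*Protocol*

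**What the plan says.** Protocol 9.8.2 sorts hypoglycemic adverse events in Parts 1 and 2 into three categories.

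- **Severe:** a measured glucose must be 49 mg/dL or less, and may come from "using plasma referenced- home glucometers, CGM (or central laboratory").
- **Documented symptomatic:** typical symptoms must be "accompanied by measured glucose ≤ 70 mg/dL using plasma-referenced home glucometers (or central laboratory").
- **Probable symptomatic:** this applies "if typical symptoms are not accompanied by a glucose determination as described above" but a low is presumed.

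SAP 7.7.1 makes hypoglycemia an adverse event of special interest. For analysis and reporting it then says that "hypoglycemia events will be limited to those in the first two categories (severe hypoglycemia and documented symptomatic hypoglycemia").

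Three other places bear on which device a Part 2 patient uses. Footnote 8 to the Part 2 Schedule of Activities says "Glucometers and related supplies will be supplied to patients who don't have CGM devices or have CGM devices that require calibration". Protocol 8.11 has patients who already own a CGM monitored by it, with "self-monitoring of blood glucose using glucometers if unblinded CGM glucose values are not available". Protocol 9.8.2 requires a reading when symptoms occur, but names no device: "Home glucose monitoring must be undertaken in the event patients experience symptoms of hypoglycemia".

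**The concern.** CGM is good enough to support the most serious category but not the next one down, and the SAP then discards what the second category cannot hold. Personal-CGM users are one of the two Part 2 randomization strata and must keep using their device throughout. A patient in that stratum who feels symptoms, looks at the CGM, sees 55 mg/dL and treats it has arguably done what the protocol asks. The event still drops out of the categorized analysis.

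Hypoglycemia is a central safety question for a drug added to insulin. A rule that loses events according to the device owned lowers the reported incidence, makes a difference between arms harder to see, and makes the two strata hard to compare.

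**Working it through.** The plan states no figure on this point, so there is none to reproduce. The check is mainly a comparison of texts.

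**Step 1. Classify each kind of event under Protocol 9.8.2, then apply SAP 7.7.1.**

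| Event | Glucose evidence | Category | In the 7.7.1 analysis? |
|---|---|---|---|
| Severe criteria met | Meter, CGM or laboratory, 49 mg/dL or less | Severe | Yes |
| Symptomatic, not severe | Meter or central laboratory, 70 mg/dL or less | Documented | Yes |
| Symptomatic, not severe | CGM only, 70 mg/dL or less | Probable | No |
| Symptomatic, not severe | No reading, low presumed | Probable | No |

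Only the third row is at issue. It holds a measured value, yet it is treated like the fourth.

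**Step 2. Who produces third-row events?** In Part 2, footnote 8 names two groups for glucometer supply: patients without a CGM and patients whose CGM needs calibration. Users of a CGM that needs none are not named, and 8.11 makes the meter their fallback. Part 1 differs. All its patients use CGM, but they receive glucometers, and Protocol 4.2 asks them to record "Home glucometer measurements undertaken in the event the patient experiences symptoms of hypoglycemia (entered in CGM as calibration"). The Part 2 text of 4.2 has no matching instruction.

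**Step 3. Can other CGM data recover these events?** Under Protocol 4.2 the sponsor's blinded CGM is the one of record in Part 2. It is worn in Weeks -2 to 0 and Weeks 10 to 12.

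- Double-blind weeks covered: 2/12 = about 17%.
- Double-blind weeks not covered (0 to 10): 10/12 = about 83%. These include the Day 1 bolus change and the first two weeks of insulin adjustment described in 8.11.

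For the uncovered weeks only the personal CGM exists, and SAP 7.6.4 leaves its use optional.

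**Step 4. Size.** Let *s* be the share of symptomatic events that arise in the personal-CGM stratum, and *u* the share of those that are non-severe with no meter or laboratory value. The share of all symptomatic events left out is *s* × *u*. The documents give neither input, so both ranges are assumptions: *s* from 25% to 75%, *u* from 20% to 80%.

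- Low end: 0.25 × 0.20 = 5%.
- High end: 0.75 × 0.80 = 60%.

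The stratum loses all its non-severe symptomatic events only if no CGM user ever takes a fingerstick or has a laboratory value.

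**The case against.** **The protocol requires home monitoring when symptoms occur, and a fingerstick makes the event documented.** This is true, and it limits the loss. Footnote 8 is a supply rule, not a bar: Protocol 3.2.2, 4.2 and the Part 2 visit sections offer glucometers as needed, and patients may own one. But the requirement names no device, so a CGM check satisfies it and still does not document the event.

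**The events are not lost from the report altogether.** This also stands in part. SAP 6.2.1 lists hypoglycemic treatment-emergent events by preferred term without a category limit, and SAP 11 lists all adverse events. SAP 7.7.2 names CGM as a source for hypoglycemia, SAP 6.1.2 counts CGM episodes at 54 and 70 mg/dL, and SAP 8.2 brings all CGM data into the evaluation of hypoglycemia. These routes do not replace the categorized count. The preferred-term table has no glucose criterion, and the SAP does not say whether the 7.7.1 limit governs it. The 6.1.2 comparison of baseline with Week 12 rests on two-week periods and carries no link to symptoms. Section 8.2 does not say whether personal CGM is included.

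**Meter confirmation may be a deliberate standard.** SAP 7.7.1 cites regulatory guidance for its limit to two categories, and CGM is less exact at low glucose. That is a fair reason to show meter-confirmed events separately. It does not explain why CGM suffices for severe events.

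**Stronger readings that a reader might infer.**

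- *All symptomatic hypoglycemia in the CGM stratum is dropped.* Not so; only row three of the table is affected among events with a measured value.
- *The comparison between arms is biased.* SAP 1.7 balances allocation within each stratum, so the expected effect is under-counting in both arms.
- *The counted events come mostly from meter users.* This depends on the inputs. With equal event rates, 70% CGM users and half of their events confirmed by meter (assumptions), CGM users supply 0.35/(0.35 + 0.30) = 54% of counted events.
- *A third-party rescue with a CGM value of 52 mg/dL escapes the severe category because of the device.* It fails the 49 mg/dL criterion on any device. The device decides only whether it is then documented or probable.

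**Conclusion.** The concern holds in a narrow form. Protocol 9.8.2 and SAP 7.7.1 together remove non-severe symptomatic events whose only glucose evidence is a CGM value of 70 mg/dL or less from the categorized hypoglycemia analysis. In Part 2 this bears on the personal-CGM stratum. The consequence is a lower count in both arms, less sensitivity to a difference, and ascertainment that varies with the device. The mechanism follows from the text alone. The 5% to 60% range rests wholly on assumed inputs and should not be read as an estimate. This is a worthwhile, inexpensive improvement to the safety analysis, not a flaw that undermines the trial's conclusions.

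**What to change.** For analysis only, and before unblinding:

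1. In SAP 7.7.1, count symptomatic events with a recorded contemporaneous CGM value of 70 mg/dL or less together with documented symptomatic events.
2. Show meter- or laboratory-confirmed events as a separate sensitivity row, and tabulate both by randomization stratum and arm.
3. State whether the 7.7.1 limit governs the preferred-term summary in SAP 6.2.1, and whether SAP 8.2 includes personal CGM, given that SAP 7.6.4 makes its use optional.
4. Reconcile the glucose sources in Protocol 9.8.2 with footnote 8 and with 8.11.

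The severe category and the treatment-discontinuation rule tied to it are not touched.

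The cost is a few lines of text and one more table. There are two limits. First, the change helps only where a CGM value was recorded with the event. Part 2 phone contacts ask about extreme episodes and give glucometer readings as the example, and personal-device data were obtained under separate consent, so some events will stay probable. Second, CGM is less exact at low glucose and detects continuously, so some events may be over-counted in the CGM stratum. That should be similar in both arms, and the sensitivity row lets the reader see it.
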